Study Design: Year two of the trial will be open-label and will include both randomized and non-randomized arms (Figure 3). Since the proposed trial design is a modification of the original protocol, the consent process will be repeated for all participants from year one of the trial. Participants from year one who received Flucelvax™ Quadrivalent or Flublok® Quadrivalent will be randomized 1:1 to receive Flucelvax™ Quadrivalent or Flublok® Quadrivalent in year two (Figure 3). Participants who received an egg-based SD vaccine in year one (Fluzone® Quadrivalent or Fluarix Quadrivalent) will be randomized 1:1:1 to receive Flucelvax™ Quadrivalent, Flublok® Quadrivalent, or Fluzone® Quadrivalent in year two.

Both sites may also aim to enroll additional participants to achieve a total of 150 participants per site (including participants who continue from year one plus additional newly enrolled participants) who received egg-based SD influenza vaccine during the 2018-2019 influenza season and who will be randomized 1:1:1 to receive Flucelvax™ Quadrivalent, Flublok® Quadrivalent, or Fluzone® Quadrivalent in year two. The KPNW site will also enroll up to 80 new participants for a non-randomized study arm that will receive Fluzone® High-Dose.

The study will prioritize enrollment of HCP who participated in a previous study of influenza vaccine effectiveness that was conducted at both study sites during the 2010-2011 influenza season. Stratified enrollment will be used for both randomized and non-randomized arms to ensure an even mix of age groups (18-44 years and 45-65 years) in each study arm.

Figure 3 Stratified randomization and sample size goals for groups with new enrollees per site

[figure not shown]
[figure not shown]

Figure 4 Study activity flow diagram, Year two

Consent/Screening/Enrollment:

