After participants are randomized, those who were in the Longitudinal PBMC Collection substudy in year one at BSWH will be invited to participate in longitudinal PBMC collection that requires collection of an additional 30mL of blood at study visits 1 and 2 in year two plus an additional study visit 1b as outlined in the original protocol. Additional participants who received either FluZone® Quadrivalent or Fluarix ® Quadrivalent in year one of the study may be recruited to maintain a total of 100 participants in the Longitudinal PBMC

Collection substudy. Participants are considered fully enrolled and contributing to the sample size goals for longitudinal PBMC collection once they have completed PBMC collection at study visits 1 and 1b in year two. KPNW will not participate in the Longitudinal PBMC Collection substudy.

Blood Draw, Vaccine Administration, Blinding, and Post-Vaccination Safety Monitoring Procedures

Same as described for year one of the trial. Information related to blood collection will be recorded on blood collection forms (Appendix S1, S2, S3, CDC HCP Flu VaxTrial: Blood Specimen Collection/Tracking Form, Year 2, Study Visits 1, 1b, and 2).

Monitoring for Adverse Events

Since the safety and tolerability of the study vaccines, including off-label use of Fluzone® High-Dose, have been established in prior studies and data from this study will not be used to seek a licensure change for Fluzone® High-Dose, data on reactogenicity events and adverse events will not be solicited. However, study staff will provide participants with a phone number to call in case they have any questions after vaccination.

Study Visit 1b of Year Two [days 6-9]

Blood Draw: Participants who had blood collected at day 0 for collection of PBMCs will be instructed to return on day 7 (acceptable range days 6-9) to have 30 ml of venous blood drawn for collection of PBMCs to assess cell-mediated immune responses to vaccination.

Study Visit 2 of Year Two [optimal timing days 21-35 (acceptable timing days 21-62)]

Blood Draw: All study participants will have 20 ml of venous blood drawn for serology testing. Participants who had blood collected at day 0 for collection of PBMCs will also have an additional 30 ml of venous blood drawn for collection of PBMCs.

Active Surveillance for Influenza-Like Illness

Active surveillance for influenza-like illness will not be conducted during year two of this trial.

Electronic Medical Record Extraction/Abstraction

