For newly enrolled participants, site investigators will extract (or abstract if necessary) data from participants' electronic medical records and state immunization registries on influenza vaccination history during the preceding ten years to include, date of receipt, vaccine product name, vaccine lot number, and route of administration (Appendix T, EMR/Chart Extraction/Abstraction Form, Year 2). Participants may be asked to sign release of medical information forms to allow access to vaccination records as needed to meet site-specific data access requirements.

For participants who were in year one of the trial, site investigators will limit extraction (or abstraction) to collecting data on influenza vaccination during the 2011-2012 and 2012-2013 influenza season.

Statistical Analysis for Year Two:

Humoral antibody responses as measured by HI (and MN, NAI and ADCC, as appropriate) at baseline (day 0) and approximately 28 days post-vaccination will be compared between participants in each study arm as outlined in Table 5; additional comparisons may be made as appropriate. Ninety-five percent confidence intervals will be calculated for relevant antibody response measures as outlined in the study endpoints at each time point (day 0 and approximately 28 days post-vaccination). Post-vaccination GMTs and MFRs at each time point post-vaccination may be compared between study arms using repeated measures mixed models with time point and vaccine as well as their interaction as independent variables; ANOVA will be used to allow for adjustment for imbalances between vaccine groups. Titers \geq seropositive thresholds at 1:40, 1:80, 1:160 and SCR may be compared with Chi Square tests. Adjustment for multiple comparisons to meet the primary objectives will be done using a Bonferroni correction approach.

Cell-mediated immune responses at baseline and approximately 7 days and 28 days will be compared between participants in each study arm. ANOVA will be used to carry out comparisons of cell-mediated immunity studies, and Bonferroni correction may be used to adjust for multiple comparisons.

All primary analyses will be conducted as intention-to-treat. All tests will be 2-tailed with a level of significance of .05.

Table 5 Planned statistical comparisons for primary objectives and endpoints in year two

Primary Objective	Comparison Group 1	Comparison Group 2

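### PBMC opt-in is sought after open-label randomisation, so acceptance can depend on the assigned year-two vaccine and bias exploratory vaccine contrasts within a year-one stratum

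*Combined protocol and SAP*

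**What the plan says.** The Study Design section states: "Year two of the trial will be open-label and will include both randomized and non-randomized arms". The section on randomisation in year two draws separate lists by year-one vaccine: 1:1 for each of the two non-egg groups and 1:1:1 for the egg-based group, each within site and age stratum.

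The section on opt-in consent for PBMC collection then sets the order of events: "After participants are randomized, those who were in the Longitudinal PBMC Collection substudy in year one at BSWH will be invited to participate". What is asked is not trivial, since taking part "requires collection of an additional 30mL of blood at study visits 1 and 2 in year two plus an additional study visit 1b". The same paragraph provides for top-up: "Additional participants who received either FluZone® Quadrivalent or Fluarix ® Quadrivalent in year one of the study may be recruited", the aim being a total of 100. It also says that participants count towards the sample size goal "once they have completed PBMC collection at study visits 1 and 1b in year two".

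On blinding, the year-two text says only "Same as described for year one of the trial". That earlier protocol is not among the documents supplied.

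The Statistical Analysis section says: "Cell-mediated immune responses at baseline and approximately 7 days and 28 days will be compared between participants in each study arm". The method is ANOVA. No step is named for selection into the subset, and the intention-to-treat statement covers primary analyses only. The cell-mediated work is listed under Exploratory Objectives.

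**The concern.** Randomisation balances the arms among everyone randomised. It balances them within a subset only if entry to that subset cannot respond to the assignment. Here the request for extra blood and an extra visit comes after assignment in an open-label study. A participant who is pleased or disappointed with the vaccine drawn may be more or less ready to accept. Staff who know the allocation may also press the invitation, or the top-up, differently by arm.

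If the people who accept then differ between arms in a trait related to cell-mediated response, the comparison mixes the vaccine effect with who agreed to take part. The contrasts at risk are those between year-two vaccines among participants with the same year-one vaccine, because those are the ones that year-two randomisation protects.

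**Working it through.** The plan gives no opt-in rate, effect size or power for this substudy, so there is no figure to reproduce. The check has two parts: the order of events, and an illustration of size on assumed inputs.

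**Order of events.** Randomisation comes first, then the PBMC invitation (with top-up in the same paragraph), then the PBMC draws at visits 1, 1b and 2, then a comparison by arm. Nothing supplied conceals the allocation until opt-in, reports opt-in by arm, or adjusts for selection.

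**Which contrasts are affected.** Lists are drawn within year-one vaccine group.
- Year-two vaccines compared within one year-one group, for example egg-based then Flucelvax against egg-based then Flublok: randomised, so exposed to selection after allocation.
- Repeated against first-time receipt, for example Flucelvax in both years against egg-based then Flucelvax: the groups come from different year-one strata, so year-two allocation did not protect this contrast. Both sides also have the same year-two vaccine, so willingness driven by that vaccine tends to cancel.

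**Scale of precision.** The PBMC site has seven randomised sequences (2 + 2 + 3); the high-dose arm is enrolled only at the other site, which does not join the substudy. Assuming equal cells, 100/7 is about 14 per group. The standard error of a two-group contrast is √(2/14) = 0.38 SD. The difference detectable with 80% power at two-sided 0.05 is (1.960 + 0.842) × √(2/14.3) = 1.05 SD.

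**Illustration A, close to a worst case (all inputs assumed).** A normal trait fully determines opt-in, and the top fraction p of each arm accepts. The mean trait among those who accept is φ(z)/p, where z cuts off the top fraction p.
- p = 0.8: 0.35 SD
- p = 0.6: 0.64 SD
- Difference between arms: 0.64 − 0.35 = 0.29 SD

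With a trait–response correlation of 0.3 the bias is 0.3 × 0.29 = 0.09 SD; with 0.5 it is 0.5 × 0.29 = 0.15 SD. Against the standard error, that is 0.09/0.38 = 0.24 to 0.15/0.38 = 0.39.

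**Illustration B, milder (all inputs assumed).** A binary trait U with 50% prevalence shifts the response by d SD. Bias = d × [P(U | opt-in, arm B) − P(U | opt-in, arm A)]. Except in the last two rows, arm A accepts at 80% whatever U is.

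| Opt-in pattern | Share with U, A and B | Bias at d = 0.3 / 0.5 / 0.8 |
|---|---|---|
| Arm B: 90% with U, 70% without | 50%, 0.9/1.6 = 56% | 0.02 / 0.03 / 0.05 SD |
| Arm B: 90% with U, 50% without | 50%, 0.9/1.4 = 64% | 0.04 / 0.07 / 0.11 SD |
| Differs by arm only (60% against 90%) | 50%, 50% | 0 |
| Differs by U only (80% with, 60% without, both arms) | 57%, 57% | 0 |

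Bias therefore needs opt-in to depend on the arm and on a response-related trait together. A difference in opt-in rates alone is not enough.

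**Pooling.** If Flucelvax and Flublok are compared across the three year-one strata, about 3 × 14.3 = 43 per arm gives √(2/43) = 0.22 SD. A bias of 0.15 SD in the same direction in every stratum would then be about 0.7 of a standard error. Pooling reduces the noise but not the bias.

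**The case against.** The strongest reply is that knowledge of the arm at the time of invitation is inferred. No section says that participants are told their vaccine before they are asked, and the blinding procedures sit in a protocol not supplied. This stands as a limit. The point rests on the open-label statement and the stated order, and shows that acceptance can depend on the arm, not that it does.

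Second, most of the invited pool was fixed by PBMC participation in year one, before year-two allocation. That narrows who is asked, but does not settle who accepts, and top-up participants are new to the substudy.

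Third, day-0 responses are collected and compared, so imbalance might be seen. With about 14 per group, however, an imbalance of 0.15 SD would not be distinguishable from chance.

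Fourth, the objective is exploratory and the illustrated bias is small beside the imprecision. Both are true, and they keep this a minor point.

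Three stronger readings are tempting and are not supported:
- A reader might infer that every cell-mediated comparison loses the protection of randomisation. The repeated versus first-time contrast, which the Background gives as the substudy's purpose, did not have that protection from year-two allocation.
- A reader might infer that people who miss visit 1b are dropped from the analysis. The sentence concerns the sample size goal, and visit 2 PBMC blood is drawn from those who gave it at day 0. No text excludes them.
- A reader might infer that limiting top-up to egg-based recipients is itself selection by arm. Year-one vaccine precedes year-two allocation, and that stratum is randomised 1:1:1. Only the timing of the request matters.

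**Conclusion.** The point holds as a minor design weakness. Asking for PBMC opt-in after open-label randomisation removes the guarantee that those who accept are comparable between year-two vaccines within a year-one stratum. It does not show that bias is present. Primary serology is unaffected.

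The size cannot be known from the documents. The range of about 0 to 0.15 SD rests on assumed opt-in rates, trait effects and correlations. The comparison with a standard error of 0.38 SD also assumes equal groups of about 14, which the plan does not promise: year one was allocated 2:2:1:1 and top-up goes only to the egg-based stratum. The whole argument assumes that the allocation is known to participants or staff when the invitation is made.

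**What to change.** 1. Ask for PBMC opt-in at the year-two consent step, before allocation is generated or disclosed, and include possible top-up participants. Consent is already being repeated for all year-one participants, so this adds no visit and no sample. Opt-in could then not depend on the year-two arm.
2. Analyse those who opted in by assigned arm within year-one stratum, using all available PBMC samples whether or not visit 1b was completed.
3. Keep the visit 1 and 1b completion rule as a recruitment tally only, and say so. Counting everyone who opted in towards the target of 100 would reduce the usable samples.
4. Report the numbers invited, accepted and completed by arm.

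The cost is a reordering of steps and the loss of one freedom: staff cannot top up thin arms after seeing the allocation. Missed draws would remain a loss after randomisation; the counts by arm make that visible but do not remove it.

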- MN responses to the *cell*-grown influenza A/H3N2 (using MDCK-SIAT or other appropriate cell line) vaccine reference viruses for each study season at approximately 28 days post-vaccination, including the following endpoints:
 - Seroconversion rate (SCR) defined as the proportion of participants with paired samples that achieved \geq 4 fold rises comparing post- versus pre-vaccination titers, and post vaccination titers \geq 40.
 - Geometric mean titers (GMT)
 - MFR mean-fold rise (MFR) defined as the ratio of the post-vaccination titer value to the pre-vaccination value
 - GMT ratio defined as the ratio of GMTs between study arms at 28 days post-vaccination
- HI responses to the *cell*-grown influenza A/H1N1, influenza B/Yamagata, and influenza B/Victoria vaccine reference viruses for each study season at approximately 28 days post-vaccination, including the following endpoints:
 - SCR
 - GMT
 - MFR
 - GMT ratio

Secondary Endpoints

- HI responses to *cell*-grown influenza A/H3N2 vaccine reference viruses for each study season at approximately 28 days, including the following endpoints
 - Post-vaccination titers \geq seropositive thresholds at 1:40, 1:80, 1:160, SCR, GMT, MFR, and GMT ratio
- HI responses to *cell*-grown influenza A/H1N1, influenza B/Yamagata, and influenza B/Victoria vaccine reference viruses for each study season at approximately 28 days, including the following endpoints
 - Post-vaccination titers \geq seropositive thresholds at 1:40, 1:80, 1:160

Exploratory Endpoints

- HI and/or MN responses to *cell*-grown *wild-type* influenza viruses at approximately 28 days (if appropriate), including the following endpoints
 - SCR, GMT, MFR, GMT ratio and post-vaccination titers \geq seropositive thresholds at 1:40, 1:80, 1:160 as measured by HI
 - SCR, GMT, MFR, and GMT ratio as measured by MN, as appropriate
- GMT as measured by NAI and ADCC pre- and post-vaccination.
- Mean percentages of strain-specific activation markers on T, B and ILC populations, frequencies of antibody secreting plasmablasts and memory B cells to hemagglutinin (HA) with HA-tags, interferon-gamma (IFN- gamma), interleukin 2 (IL-2), and Tumor Necrosis Factor-alpha (TNF-alpha) secreting T

cell responses to *wild-type* cell-grown strains, B cell repertoire, antibody-seq, fine-specificities of antibody reactivities and single cell transcriptome analysis (where feasible) at approximately 7 and 28 days post-vaccination.

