Participants who present with moderate to severe illness with fever and/or acute illness during the study visit will not receive study vaccine until their illness has resolved. In this case, a follow-up appointment will be made after resolution of the illness, at which time the participant will receive the vaccine.

Randomization of Participants in Year two of the Study

Study nurses administering vaccine will consult participants' study files to confirm which study vaccine participants from year one received during the first year of the study. For the purposes of randomization, newly enrolled participants into the main trial who did not participate in year one will be treated as part of the group who received FluZone® Quadrivalent or Fluarix ® Quadrivalent during year one.

Stratified block randomization will be used at each site to ensure even allocation of age groups (18-44 years and either 45-65 years) to each study arm (Figure 3). Within each age stratum:

- participants who received Flucelvax™ Quadrivalent in year one will be randomized 1:1 to receive one 0.5 mL intramuscular dose Flucelvax™ Quadrivalent or Flublok® Quadrivalent;
- participants who received Flublok® Quadrivalent in year one will be randomized 1:1 to receive one 0.5 mL intramuscular dose of Flucelvax™ Quadrivalent or Flublok® Quadrivalent; and
- participants who received FluZone® Quadrivalent or Fluarix ® Quadrivalent in year one or who were newly enrolled into the main trial will be randomized 1:1:1 to receive one 0.5 mL intramuscular dose of Flucelvax™ Quadrivalent, Flublok® Quadrivalent , or FluZone® Quadrivalent.

Randomization lists will be generated using a computerized random-number generator to select randomly permuted group blocks of six with either three in each block assigned to Flucelvax™ Quadrivalent and Flublok® Quadrivalent for those who received Flucelvax™ Quadrivalent or Flublok® Quadrivalent in year one or two in each block assigned to FluZone® Quadrivalent or Flucelvax™ Quadrivalent or Flublok® Quadrivalent for those who received FluZone® Quadrivalent in year one or are newly enrolled to the main trial in year two. The next available sequential study-number will be assigned to each enrolled participant upon study-entry.

Participants who are newly enrolled into the FluZone® High-Dose substudy will not be randomized and will all receive FluZone® High-Dose.

'Opt-In Consent for Longitudinal PBMC Collection:

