Compare immune responses after two consecutive years of vaccination with cell-based influenza vaccine (Flucelvax™ Quadrivalent) or recombinant influenza vaccine (Flublok® Quadrivalent) versus first time receipt of these vaccines following vaccination with SD egg-based influenza vaccines.	Flucelvax™ Quadrivalent year one/year two	SD egg-based vaccine year one/Flucelvax™ Quadrivalent year two
	Flublok® Quadrivalent year one/year two	SD egg-based vaccine year one/Flublok® Quadrivalent year two
Compare immune responses after two consecutive years of vaccination with cell-based influenza vaccine (Flucelvax™ Quadrivalent), recombinant influenza vaccine (Flublok® Quadrivalent), or SD egg-based vaccine (Fluzone SD).	Flucelvax™ Quadrivalent year one/year two	SD egg-based vaccine year one/year two
	Flublok® Quadrivalent year one/year two	SD egg-based vaccine year one/year two

Compare immune responses after cell culture-based influenza vaccine (Flucelvax™ Quadrivalent) versus recombinant influenza vaccine (Flublok® Quadrivalent) at approximately 28 days after receipt of the 2019-2020 vaccines, regardless of prior vaccination status.	Flucelvax™ Quadrivalent year 2 (regardless of year one vaccine)	Flublok® Quadrivalent year 2 (regardless of year one vaccine)
Compare immune responses after first time vaccination with cell-based influenza vaccine (Flucelvax™ Quadrivalent), recombinant influenza vaccine (Flublok® Quadrivalent), or high-dose egg-based vaccine (Fluzone High-Dose) following vaccination with SD egg-based influenza vaccines to repeated vaccination with SD egg-based vaccine.	SD egg-based vaccine year one/Flucelvax™ Quadrivalent year two SD egg-based vaccine year one/Flublok® Quadrivalent year two Fluzone HD year two	SD egg-based vaccine year one/year two

SD: Standard dose; HD: High dose

Power/Sample Size Calculations:

Study sample size was determined based on available resources. An overall sample size of up to 830 with

- 90 participants each in the Flublok® Quadrivalent year one/ Flucelvax™ Quadrivalent year two group and Flublok® Quadrivalent year one/year two group
- 135 participants each in the Flucelvax™ Quadrivalent year one/year two group and Flucelvax™ Quadrivalent year one/ Flublok® Quadrivalent year two group
- 100 participants each in the SD (SD) egg-based vaccine year one/Flucelvax™ Quadrivalent year two, SD egg-based vaccine year one/Flublok® Quadrivalent year two, and SD egg-based vaccine year one/year two groups, and

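### Day-0 titer and the randomisation factors are not fixed as covariates, so the three contrasts randomised in year two give up a modest gain, mainly in interval width

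*Combined protocol and SAP*

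**What the plan says.** Under Statistical Analysis for Year Two, the titer model is given as "repeated measures mixed models with time point and vaccine as well as their interaction as independent variables". Its use is optional, since the plan says: "Post-vaccination GMTs and MFRs at each time point post-vaccination may be compared between study arms". Adjustment is mentioned only once: "ANOVA will be used to allow for adjustment for imbalances between vaccine groups". No covariate is named there or elsewhere in the amendment, and nothing says what counts as an imbalance. For the binary endpoint, "SCR may be compared with Chi Square tests".

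The Primary Endpoints list GMT, GMT ratio, SCR and MFR, the last as "MFR mean-fold rise (MFR) defined as the ratio of the post-vaccination titer value to the pre-vaccination value". Day-0 titer thus enters as a time point and as the MFR denominator only.

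Under Randomization of Participants in Year two of the Study, "Stratified block randomization will be used at each site to ensure even allocation of age groups", and this is done separately by year-one vaccine group. High-dose participants "will not be randomized and will all receive FluZone® High-Dose".

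**The concern.** A model with time point, vaccine and their interaction leaves the day-0 means free in each arm. With complete pairs, its day-28 contrast is the raw GMT ratio and its interaction contrast is the raw MFR ratio. Under randomisation both estimate the same log ratio, but neither uses day-0 titer efficiently. The raw contrast ignores it. The MFR contrast subtracts it in full, which adds noise when the correlation between visits is low. Conditioning on it as a covariate avoids both problems.

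The plan says that sample size was set by resources and divides alpha by up to eight, so precision cannot easily be bought with participants. The covariates are already collected. Naming them in advance would also remove a choice otherwise made after imbalances are seen.

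The point is confined to three of the eight Table 5 contrasts: Flucelvax v Flublok (objective 2), and first-time Flucelvax and first-time Flublok v repeat standard-dose egg-based vaccine (objective 4). Four others compare across year-one groups, and the high-dose contrast is not randomised.

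**Working it through.** **Inputs from the documents.** Two-sided alpha 0.05, divided by 8 for Table 6, gives 0.00625. The target GMT ratio is 1.2 (ln 1.2 = 0.1823). The two objective 4 contrasts have 100 v 100. Objective 2 has 135 + 90 + 100 = 325 per arm, with equal allocation to Flucelvax and Flublok inside every year-one group.

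**Assumptions.** The documents give neither the SD of ln titer, nor the power, nor the day-0/day-28 correlation r. Power is taken as 80%, r as 0.4 to 0.7, and the SDs at the two visits as equal, except where varied below.

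**Reproducing Table 6.** A two-sample t test on ln titer with alpha 0.00625, 80% power and SD 0.2935 returns 16, 22, 34, 69 and 245 per group for ratios 1.5 to 1.1, which matches every row. The fit is not unique: 90% power with SD 0.2615 also matches exactly.

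**Variance relative to the raw day-28 contrast.** MFR: 2(1 - r). ANCOVA: 1 - r². Power is for 100 v 100, ratio 1.2, SD 0.2935, where the raw contrast has 94.7%.

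| r | MFR variance | ANCOVA variance | ANCOVA / better planned | Interval narrower v raw | Interval narrower v better planned | Power, MFR | Power, ANCOVA |
|---|---|---|---|---|---|---|---|
| 0.4 | 1.20 | 0.84 | 0.84 | 8.3% | 8.3% | 89.2% | 97.8% |
| 0.5 | 1.00 | 0.75 | 0.75 | 13.4% | 13.4% | 94.7% | 98.9% |
| 0.6 | 0.80 | 0.64 | 0.80 | 20.0% | 10.6% | 98.3% | 99.7% |
| 0.7 | 0.60 | 0.51 | 0.85 | 28.6% | 7.8% | 99.8% | 100.0% |

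MFR is worse than the raw contrast below r = 0.5 and better above it. A simulation of 20,000 trials of 100 v 100 per value of r agreed: ANCOVA/raw was 0.845, 0.747, 0.651 and 0.511. In a separate simulation at r = 0.5 with four strata, all estimates were unbiased. Type I error at nominal 0.00625 was 0.0053 unadjusted and 0.0065 adjusted.

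**On the ratio scale.** The 95% half-width factor is exp(1.96 × SD × √(2/n)) for the raw contrast. At n = 100 this is exp(1.96 × 0.2935 × √0.02) = 1.085. Multiplying the SD by √0.75 (ANCOVA, r = 0.5) gives 1.073. At r = 0.7 the better planned contrast (MFR) gives 1.065 and ANCOVA 1.060. The smallest ratio with 80% power is 1.162 raw and 1.147 to 1.113 with ANCOVA over r = 0.4 to 0.7. For 325 v 325 the factor goes from 1.046 raw to 1.042-1.033 with ANCOVA, and power for 1.2 is about 100% under any method.

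**Unequal SDs.** If the day-0 SD is k times the day-28 SD, the MFR factor is 1 + k² - 2rk. For k = 0.8, the ANCOVA variance saving over the better planned contrast is 16, 11, 6 and 2% at r = 0.4 to 0.7 (intervals 8% down to 1% narrower). For k = 1.25 it is 16, 25, 36 and 37% (8 to 21% narrower).

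**Larger SD.** At an assumed SD of 0.5, 100 v 100, ratio 1.2, power is 42.8% raw, 34.4/42.8/54.8/71.3% for MFR and 52.1/58.5/67.7/80.0% for ANCOVA. That is 9 to 16 points above the better planned contrast.

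**SCR.** The gain cannot be computed from the documents. As an illustration, take two equal strata with rates of 20% and 40%. The mean is 30%, total variance 0.30 × 0.70 = 0.21, and between-stratum variance 0.10² = 0.01. The share explained is 0.01/0.21 = 4.8%, so the interval narrows by 1 - √0.952 = 2.4%.

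**The case against.** The planned comparisons are valid. GMT ratio and MFR are the named endpoints and the model estimates both, so this is a matter of efficiency and not an error. On the ratio scale the gain over the better planned contrast is about one percentage point or less at 100 per arm, and objective 2 gains almost nothing that matters. Neither r nor the SD is in the documents. The chosen range of r surrounds the point of largest gain over the better planned contrast; with equal SDs that gain is only 2.0% in interval width at r = 0.2, 4.6% at 0.3, 5.1% at 0.8 and 2.5% at 0.9. With the alternative fit to Table 6 (SD 0.2615), raw power is already 98.4%. The SCR gain looks negligible. Year-one methods carry over unless changed (METHODS, YEAR TWO MODIFICATIONS), so the original protocol may already list covariates. Finally, the repeat standard-dose arm would be summarised by different models in objectives 3 and 4.

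Most of this stands as a limit on size. It does not remove the point: with equal SDs, ANCOVA is more precise than both planned contrasts for any r between 0 and 1, and it uses data already in hand. The mixed set of models has a reason. In objectives 1 and 3 the year-two day-0 titer follows the year-one vaccine being compared, so adjusting for it there could remove part of the effect. That is why the covariates should be stated contrast by contrast.

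**Conclusion.** The concern holds as a modest, inexpensive improvement for three contrasts. With r between 0.4 and 0.7 and equal SDs, intervals would be 8-29% narrower than for the raw GMT ratio, which is the powered endpoint, and 8-13% narrower than for whichever planned contrast is better. The second range widens to 1-21% if the two SDs differ by a factor of 0.8 or 1.25. At the SD implied by Table 6, power for a ratio of 1.2 barely moves; it would move only if titers vary more than Table 6 implies. Validity is not in question. All of this rests on assumed r and SD, on 80% power for the back-calculation, and on the original protocol, which was not supplied, not already fixing covariates.

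**What to change.** For the three contrasts named above, pre-specify ANCOVA on ln day-28 titer with vaccine, ln day-0 titer, site and age stratum, adding year-one vaccine group for objective 2 only. The same adjusted contrast serves GMT ratio and MFR ratio, since subtracting ln day-0 titer from the outcome leaves the vaccine coefficient unchanged. Unadjusted GMTs and MFRs can still be reported. Compare SCR by a Mantel-Haenszel risk difference, or a CMH test, stratified by the same randomisation factors.

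State that objectives 1 and 3 are not adjusted for year-two day-0 titer, and why. The non-randomised high-dose contrast is outside this recommendation. If the original protocol already fixes covariates, cite them in Statistical Analysis for Year Two.

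The cost is SAP wording, plus a sentence explaining why the models differ between objectives. No new data or participants are needed.
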